## **20. APPENDIX B: CALCULATION OF MODIFIED RODNAN SKIN SCORE**

[figure not shown]
The mRSS is displayed below:

[figure not shown]

## 21. APPENDIX C: SCLERODERMA HEALTH ASSESSMENT QUESTIONNAIRE

The SHAQ-DI is displayed below:

Source: <https://eprovide.mapi-trust.org/instruments/scleroderma-health-assessment-questionnaire>

## 22. APPENDIX D: PHYSICIAN GLOBAL ASSESSMENT

KD025  
Protocol Number KD025-215

IND 140383

### Physician Global Assessment

Physician Global Assessment  
Visual Analog Scale

*Please mark on the scale below a vertical line anywhere between the two ends corresponding to your overall health during the last week.*

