**How was your overall health during the last week?**

## 23. APPENDIX E: PATIENT GLOBAL ASSESSMENT

KD025  
Protocol Number KD025-215

IND 140383

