3.1.6 Handling of Incomplete or Missing Data

There will be no imputation for missing efficacy values. Missing start and end dates for AE and concomitant medication (CM)

The assumption will be the worst or most conservative judgment when imputing AE and CM start and end dates. The purpose of imputing a start date is to help define whether the AE/CM started while taking study drug.

For a partial or missing start date:

- If the day is missing, the first day of the month will be imputed. If the missing day is the same as the month of first dose of study drug, then the first dose date will be imputed.
- If the day and month are missing, the first day of January will be imputed. If the year is the same as the first dose date, then the first dose date will be imputed.
- If the day is completely missing, the first dose date will be imputed. If the end date suggests it could have started prior to this, the first day of January of the same year as the end date will be imputed.
- When imputing a start date, the start date will ensure that the new imputed date is sensible, i.e., is prior to the end date of the AE or CM.

For a partial or missing end date:

- If the day is missing, the last day of the month or the last assessment date, whichever is earlier, will be imputed.
- If the day and month are missing, the 31st of December or the last assessment date, whichever is earlier, will be imputed.
- If the date is completely missing, there will be a need to look at whether the AE/CM is still ongoing before imputing a date. If the ongoing flag is missing, then it will be assumed that AE is still present, or CM is still being taken (i.e., do not impute a date). If the AE/CM has stopped, then the last assessment date will be imputed.

These data imputations are for categorization purpose only and will not be used in listings.

If the assessment of the relationship of the AE to belumosudil is missing, then it will be assumed that the AE is related to belumosudil and the AE considered as such in the frequency tables of possibly related AEs. No imputation should be done at the data level.

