3.8 Definition of Efficacy Endpoints

3.8.1 Primary Efficacy Endpoint: CRISS

The primary efficacy endpoint is Combined Response Index in Diffuse Cutaneous Systemic Sclerosis (CRISS).

CRISS is a 2-step process for use in a clinical trial.

Step 1: patients who develop new onset of renal crisis, new onset or worsening of lung fibrosis, new onset of pulmonary arterial hypertension, new onset of left ventricular failure during the trial are considered as not improved and assigned a probability of improving equal to 0.0.

Step 2: For the remaining patients, step 2 involves computing the predicted probability of improving for each individual, using the equation shown below.

$$\frac{\exp[-5.54 - 0.81 * \Delta_{MRSS} + 0.21 * \Delta_{FVC\%} - 0.40 * \Delta_{Pt-glob} - 0.44 * \Delta_{MD-glob} - 3.41 * \Delta_{HAQ-DI}]}{1 + \exp[-5.54 - 0.81 * \Delta_{MRSS} + 0.21 * \Delta_{FVC\%} - 0.40 * \Delta_{Pt-glob} - 0.44 * \Delta_{MD-glob} - 3.41 * \Delta_{HAQ-DI}]}$$

where Δ_{MRSS} indicates the change in mRSS from baseline to follow up, $\Delta_{FVC\%}$ denotes the change in FVC% predicted from baseline to follow up, $\Delta_{Pt-glob}$ indicates the change in patient global assessment, $\Delta_{MD-glob}$ denotes the change in physician global assessment, and Δ_{HAQ-DI} is the change in HAQ-DI. All changes are absolute change (Time₂-Time_{baseline}).

As patient global assessment and physician global assessment are based on a VAS of 0 (Extremely Poor)-100 (Excellent) in CRF. When calculating the CRISS score, these 2 scores should be divided by 10 firstly to make it in a 0-10 scale.

The outcome is a continuous variable between 0.0 and 1.0 (0-100%). A higher score indicates greater probability of improvement. A CRISS score $\geq 20\%$ is considered as the minimal detectable difference and will be described as CRISS20 in the SAP. A CRISS score $\geq 60\%$ is considered as the minimally important difference and will be described as CRISS60 in the SAP. This will be the primary variable for efficacy.

Analysis of the primary efficacy endpoint will be conducted using the mITT population. The number and percentage of patients achieving CRISS60 response at week 24 will be summarized.

The following analysis on CRISS will also be provided as supportive evidence for the primary analysis.

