3.8.2.4 Physician Global Assessment

Physician global assessment is physician's assessment of patient's overall health during the last week based on a VAS of 0 (Extremely Poor)-100 (Excellent). A positive change from baseline demonstrates improvement.

Physician global assessment score, change from baseline, percent improvement will be summarized as a continuous endpoint at all scheduled assessment visits.

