3.8.2.5 Patient Global Assessment

Patient global assessment is patient's assessment of their overall health during the last week based on a VAS of 0 (Extremely Poor)-100 (Excellent). A positive change from baseline demonstrates improvement.

Patient global assessment score, change from baseline, percent improvement will be summarized as a continuous endpoint at all scheduled assessment visits.

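### The Physician Global Assessment form in Protocol Appendix D asks about the rater's own health, which does not match the SAP definition of this CRISS component (minor wording defect; misrecorded data not shown)

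*Protocol*

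**What the plan says.** **Protocol Appendix D (physician form).** Under the title Physician Global Assessment, the instruction reads "Please mark on the scale below a vertical line anywhere between the two ends corresponding to your overall health during the last week". The question printed with the scale, before the Appendix E heading, is "How was your overall health during the last week".

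**Protocol Appendix E (patient form).** The instruction and the question are word for word the same. Only the title differs.

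**SAP definitions.** Section 3.8.2.4 states "Physician global assessment is physician's assessment of patient's overall health during the last week". Section 3.8.2.5 states "Patient global assessment is patient's assessment of their overall health during the last week". These are two raters and two items, both about the same person, the patient.

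**Use in the analysis.** Protocol sections 6.1, 6.1.2 and 9.8.2 list the physician global as a secondary endpoint. SAP section 3.8.1 also puts its change from baseline into Step 2 of CRISS, with a coefficient of -0.44. That section says the two global scores "are based on a VAS of 0 (Extremely Poor)-100 (Excellent) in CRF" and that "these 2 scores should be divided by 10 firstly to make it in a 0-10 scale". The number and percentage of subjects reaching CRISS60 at Week 24 is the primary summary. Subjects with a Step 1 organ event "are considered as not improved and assigned a probability of improving equal to 0.0", so their score does not use the physician global.

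**Elsewhere in the protocol.** Section 6.1 explains how mRSS, SHAQ-DI and FVC are measured but does not say what the physician global measures. The visit lists in section 5 and the schedule in Appendix A only name it.

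**The concern.** A physician who follows the Appendix D text literally is asked about the physician's own health. If the form is handed to the patient because the question addresses the patient, it collects a second self-rating. Neither is the item that the SAP defines.

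The two readings would do different things to CRISS:

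- If physicians rated themselves, the term would carry no information about the patient.
- If patients completed the form, their own view would enter twice, once with the -0.40 weight and once with the -0.44 weight, and the physician's view would be lost.

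The form is scheduled at baseline and at every efficacy visit, across 5 to 6 centers, so sites could also read it differently. What could be affected is the physician global summary and, through Step 2, the CRISS score and the CRISS60 percentage. The study is exploratory (Protocol 9.7.2) and its endpoints are summarised descriptively (Protocol 9.8.4), so no formal test is involved.

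**Working it through.** **1. Texts side by side**

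| Source | Rater | Whose health |
|---|---|---|
| Appendix D, form text | physician, by the title | the person addressed, so literally the physician |
| Appendix E, form text | patient, by the title | the person addressed, so the patient |
| SAP 3.8.2.4 | physician | the patient |
| SAP 3.8.2.5 | patient | the patient |

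Appendix E agrees with SAP 3.8.2.5. Appendix D does not agree with SAP 3.8.2.4. The scale graphic is missing from the extracted text, but the instruction and the question are present, and the comparison needs only those.

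**2. Weight of the item in CRISS**

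The documents state no error size and no figure to reproduce, so what follows is an illustration over an assumed range. Inputs from SAP 3.8.1: coefficient 0.44 in absolute value per point on the 0-10 scale, VAS divided by 10, cut-off 0.60. Sample size 12 to 15 (Protocol 3.2).

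The error that matters is the error in the change from baseline. A misrating of the same size at both visits cancels.

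- Shift of the CRISS logit for an error of d mm in the change: 0.44 x d/10.
- mRSS points with the same effect: shift / 0.81.
- Logit of the cut-off: ln(0.60/0.40) = 0.405.
- Error-free scores that could cross the cut-off: expit(0.405 - shift) to expit(0.405 + shift), where expit(x) = 1/(1 + exp(-x)).

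| Assumed error d | Logit shift | mRSS equivalent | Error-free CRISS that could cross 0.60 |
|---|---|---|---|
| 10 mm | 0.44 | 0.54 | expit(-0.035) to expit(0.845) = 0.49 to 0.70 |
| 20 mm | 0.88 | 1.09 | expit(-0.475) to expit(1.285) = 0.38 to 0.78 |
| 30 mm | 1.32 | 1.63 | expit(-0.915) to expit(1.725) = 0.29 to 0.85 |

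Each band holds for an error in either direction, and it stays the same if the sign of the term is reversed.

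One case shows how much depends on d. Take a subject with an error-free score of 0.75 (logit 1.099) and an adverse error. At 10 mm the score is expit(1.099 - 0.44) = 0.66, still a responder. At 20 mm it is expit(1.099 - 0.88) = 0.55, no longer one.

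**3. Effect on the reported rate**

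One reclassified subject moves the CRISS60 rate by 1/15 = 6.7 points or 1/12 = 8.3 points. The documents do not allow an estimate of how many Step 2 subjects lie in any band. Step 1 subjects stay at 0.0 whatever the form records.

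**The case against.** The strongest reply is that this is a copying slip in an appendix and that nobody would be misled. The title on the form names the rater, the visit lists schedule the physician and patient items separately, and an investigator scoring their own health as a subject's efficacy outcome is implausible. The SAP states the intended item clearly. The SAP also takes the scale from the CRF, which is not among the documents, so the wording that sites saw is unknown.

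Most of this stands. It makes the intent fairly clear and leaves misuse unproven. It does not remove the mismatch: a title identifies who rates but does not change what the instruction asks. The SAP is an analysis document and does not instruct sites. Appendix D is the protocol's only statement of what the physician is asked.

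A reader might go further and infer that the physician global data are wrong, that the CRISS60 result is therefore unreliable, or that a sensitivity analysis with alternative denominators is already needed. The documents do not support any of these. Each needs two facts that are not shown: that the faulty wording reached the forms in use, and that raters followed it. A reader might also take the 10 mm band as a limit on the damage. It is not one, because the band and the outcome for a subject at 0.75 both change at 20 mm, and the documents give no basis for choosing a value.

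**Conclusion.** The point holds as a minor wording defect in the instrument. The physician form repeats the patient form's text and does not match the SAP definition of the item. This rests on direct comparison of the texts and is certain.

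Any effect on data is possible but not shown. If errors occurred, their reach through CRISS is limited to Step 2 subjects. For assumed errors of 10 to 30 mm in the change, the subjects at risk of reclassification are those with an error-free CRISS from about 0.49-0.70 up to about 0.29-0.85, at 6.7 to 8.3 points of the CRISS60 rate each. The error sizes are assumptions and the number of such subjects is unknown. No test, sample size, population or analysis rule changes.

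**What to change.** - Reword the Appendix D instruction and question so that the physician is asked to rate the patient's overall health during the last week. Make the same change on any matching source form or eCRF page.
- Check the wording actually used at sites.
- Only if the faulty wording was used, query who completed the forms and whose health was rated, and report the number affected.

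The cost is one sentence, one question and a check of the source and eCRF text, with a data query only if that check finds the faulty wording in use. Subjects undergo no new procedure.

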**How was your overall health during the last week?**

## 23. APPENDIX E: PATIENT GLOBAL ASSESSMENT

KD025  
Protocol Number KD025-215

IND 140383

### Patient Global Assessment

Patients Global Assessment  
Visual Analog Scale

*Please mark on the scale below a vertical line anywhere between the two ends corresponding to your overall health during the last week.*

**How was your overall health during the last week?**

## 24. APPENDIX F: DETERMINING RELATIONSHIP OF ADVERSE EVENTS TO STUDY DRUG

Determination the relationship of AEs to study drug is displayed below:

### 1 NOT RELATED

This category applies to those AEs, which, after careful medical consideration, are clearly felt to be due to extraneous causes (e.g., disease, environment, etc.) that are unrelated to the administration of study drug.

### 2 UNLIKELY RELATED (must have first 2)

This category applies to those AEs, which, after careful medical consideration, are felt unlikely to be related to the administration of the study drug. The relationship of an AE to the study drug can be considered unlikely if:

- It does not follow a reasonable temporal sequence from administration of the drug.
- It could readily have been a result of the subject's clinical state, environmental or toxic factors, or other modes of therapy administered to the subject.
- It does not follow a known response pattern to the suspected drug.
- It does not reappear or worsen when the drug is re-administered.

### 3 POSSIBLY RELATED (must have first 2)

This category applies to those AEs, which, after careful medical consideration, are felt unlikely to be related to the administration of the study drug, but the possibility cannot be ruled out with certainty. The relationship of an AE to the study drug can be considered possible if:

- It follows a reasonable temporal sequence from administration of the drug.
- It could readily have been a result of the subject's clinical state, environmental or toxic factors, or other modes of therapy administered to the subject.
- It follows a known response pattern to the suspected drug.

### 4 PROBABLY RELATED (must have first 3)

This category applies to those AEs, which, after careful medical consideration, are felt with a high degree of certainty to be related to the administration of the study drug. The relationship of an AE to the study drug can be considered probable if:

- It follows a reasonable temporal sequence from administration of the drug.
- It could not be reasonably explained by the known characteristics of the subject's clinical state, environmental or toxic factors or other modes of therapy administered to the subject.
- It disappears or decreases upon cessation of drug or reduction in dose.\*
- It follows a known response pattern to the suspected drug.

**5 DEFINITELY RELATED** (must have first 3)

This category applies to those AEs, which, after careful medical consideration, are felt to be related to the administration of the study drug. The relationship of an AE to the study drug can be considered related if:

- It follows a reasonable temporal sequence from administration of the drug or drug levels have been established in body fluids or tissues.
- It could not be reasonably explained by the known characteristics of the subject's clinical state, environmental or toxic factors or other modes of therapy administered to the subject.
- It disappears or decreases upon cessation of drug or reduction on dose and appears upon rechallenge.\*
- It follows a known response pattern to the suspected drug.

\*There are exceptions when an AE does not disappear upon discontinuation of the drug, yet drug relatedness clearly exists.

## 25. APPENDIX G: DRUGS THAT INDUCE AND INHIBIT CYP3A4

This is not a comprehensive list, and all concomitant medications should be evaluated for possible interactions with belumosudil.

**Examples of Clinical Inducers / Inhibitors of CYP3A4**

	Strong	Moderate	Weak
Inducers	Carbamazepine Enzalutamide Mitotane Phenytoin Rifampin St. John's wort	Bosentan Efavirenz Etravirine Modafinil	Armodafinil Rufinamide
Inhibitors	Boceprevir Cobicistat Conivaptan Danoprevir Dasabuvir Elvitegravir Grapefruit juice Indinavir Itraconazole Ketoconazole Lopinavir Paritaprevir Ombitasvir Posaconazole Ritonavir Saquinavir Telaprevir Tipranavir Troleandomycin Voriconazole	Aprepitant Cimetidine Ciprofloxacin Clotrimazole Crizotinib Cyclosporine Dronedarone Erythromycin Fluconazole Fluvoxamine Imatinib Tofisopam Verapamil	Chlorzoxazone Cilostazol Fosaprepitant Istradefylline Ivacaftror Lomitapide Ranitidine Ranolazine Tacrolimus Ticagrelor

## 26. APPENDIX H: DRUGS KNOWN TO HAVE THE POTENTIAL FOR QTC PROLONGATION

Drugs known to have the potential for prolonging of QTc are prohibited. The list below is not comprehensive. All concomitant medications should be evaluated for possible interactions with belumosudil.

Generic Name	
• Aclarubicin	• Iloperidone
• Amiodarone	• Levofloxacin
• Anagrelide	• Levomepromazine
• Arsenic trioxide	• Levomethadyl acetate
• Astemizole	• Levosulpiride
• Azithromycin	• Mesoridazine
• Bepridil	• Methadone
• Chloroquine	• Moxifloxacin
• Chlorpromazine	• Ondansetron
• Cilostazol	• Oxaliplatin
• Ciprofloxacin	• Papaverine HCl
• Cisapride	• Pentamidine
• Citalopram	• Pimozide
• Clarithromycin	• Probuconol
• Disopyramide	• Procainamide
• Dofetilide	• Propofol
• Domperidone	• Quinidine
• Donepezil	• Roxithromycin
• Dronedarone	• Sevoflurane
• Droperidol	• Sotalol
• Erythromycin	• Sparfloxacin
• Escitalopram	• Sulpiride
• Flecainide	• Sultopride
• Fluconazole	• Terfenadine
• Gatifloxacin	• Terlipressin
• Grepafloxacin	• Terodilidine
• Halofantrine	• Thioridazine
• Haloperidol	• Vandetanib
• Ibogaine	
• Ibutilide

CRISS	Combined Response Index in Diffuse Cutaneous Systemic Sclerosis
CTCAE	Common Terminology Criteria for Adverse Events
dcSSc	Diffuse cutaneous systemic sclerosis
DL _{CO}	Diffusing capacity of the lungs for carbon monoxide
ECG	Electrocardiogram
EOT	End of Treatment
FEV ₁	Forced expiratory volume (in the first second)
FVC	Forced vital capacity
GFR	Glomerular filtration rate
GGT	Gamma-glutamyl transferase
Hb	Hemoglobin
HLGT	High level group term
HRCT	High-resolution computerized tomography
IEC	Independent Ethics Committee
ILD	Interstitial lung disease
IND	Investigational New Drug
IRB	Institutional review board
ICH	International Conference on Harmonisation
MedDRA	Medical Dictionary for Regulatory Activities
miITT	Modified intent-to-treatment
MMRM	Mixed-effects Model of Repeated Measures
[name]
mRSS	Modified Rodnan Skin Thickness Score
PA	Primary analysis

PD	Pharmacodynamic
PDI	Planned dose intensity
PE	Physical exam
PFTs	Pulmonary function tests
PK	Pharmacokinetic
PT	Preferred term
QD	Once daily
QTcF	Corrected QT interval using Fridericia's formula
RDI	Relative dose intensity
RV	Residual volume
SAE	Serious adverse event
SAP	Statistical analysis plan
SD	Standard deviation
SHAQ-DI	Scleroderma Health Assessment Questionnaire-Disability Index
SOC	System organ class
SSc	Systemic sclerosis
TEAE	Treatment emergent adverse event
TLC	Total lung capacity
VAS	Visual Analog Scale
WHO	World Health Organization

1 INTRODUCTION

This Statistical Analysis Plan (SAP) describes data-handling and statistical procedures to be used for Study KD025-215/ACT17634 as specified in protocol (Amendment No. 2, 01 July 2021): A Phase 2, Open-label Multicenter Study to Evaluate the Efficacy and Safety of Belumosudil in Subjects with Diffuse Cutaneous Systemic Sclerosis (dcSSc)

Exploratory objectives analyses (biomarkers analysis, histology and gene expression analyses) will be described in separate documents.

The SAP was written in accordance with the recommendations outlined in the International Conference on Harmonisation (ICH) E9 Guideline entitled “Guidance for Industry: Statistical Principles for Clinical Trials” and the most recent ICH-E3 Guideline, entitled “Guidance for Industry: Structure and Content of Clinical Study Reports.”

2 STUDY SUMMARY

2.1 Study Objectives

2.1.1 Primary objective

- To evaluate the efficacy of belumosudil using the Combined Response Index in diffuse cutaneous Systemic Sclerosis (CRISS) at Week 24.

2.1.2 Secondary objectives

- To assess the CRISS at Weeks 8, 16, 36 and 52
- To evaluate the efficacy of belumosudil at Week 24 for:
 - Modified Rodnan skin thickness score (mRSS)
 - Forced vital capacity (FVC)
 - Physician global assessment
 - Patient global assessment
 - Scleroderma Health Assessment Questionnaire-Disability Index (SHAQ-DI)
- To evaluate the efficacy of belumosudil at Weeks 8, 16, 36 and 52 compared to baseline for all subjects for the parameters in the bullet above
- To assess the safety of belumosudil in subjects with diffuse cutaneous systemic sclerosis (dcSSc) by examining the percentage of subjects with Treatment-emergent AEs (TEAEs) (Common Terminology Criteria for Adverse Events [CTCAE] v5.0)

2.2 Study Design

KD025-215/ACT17634 is a Phase 2, open-label, multicenter trial in subjects with dcSSc.

Subjects who have signed an Institutional Review Board/Independent Ethics Committee-approved informed consent form and met all of the inclusion/exclusion criteria will be enrolled. A total of 12-15 subjects will receive orally administered belumosudil 200 mg twice daily (BID) for 52 weeks. Study drug will be collected at the end of Week 52. The primary endpoint will be analyzed using Week 24 data.

Efficacy will be assessed at baseline and throughout the 52 weeks of the treatment period using CRISS, mRSS, pulmonary function tests (PFTs), Physician Global Assessments, and Patient Global Assessments. Safety will be assessed throughout the study.

Subjects will undergo evaluations as outlined in the Study Assessment table. A 4-Week Follow-Up visit will occur 28 days (\pm 3 days) after the last dose of study drug.

Efficacy will be assessed throughout the 52-week dosing period using CRISS, mRSS, PFTs, physician global assessment, SHAQ-DI.

